During the second phase (Aim 2) fifty participants will be recruited, enrolled and randomized 1:1 to either the Standard of Care (Control) Group or the Intervention Group. Participants in both groups will be compensated up to a total of \$250 for travel, lost wages, and time. ClinCards will be given to each participant and payments for each of the 4 data collection visits will be uploaded after the assessments that are assigned to each respective visit are completed. They will receive: \$50 for completing all baseline assessments, \$50 for completing all 4 week assessments, \$100 for completing all 12 week assessments, and \$50 for completing all 24 week assessments. Payments will be prorated for completing questionnaires, biospecimens, BP measurements, and dietary recalls at each visit.

Participants who consent for Aim 2 will have the option of sharing their experiences and thoughts about participating in research with the Duke Research Equity and Diversity Initiative (READI) project. The READI project aims to better understand and improve participants' experiences in research studies.

Participants will indicate on the consent form whether they agree to share their contact information (name and email address) with the READI project, or not. If they do, they will be invited to share the information on their experience through surveys.

Participants enrolled and randomized in Aim 2 will have the option to choose to have additional blood samples collected and stored for future research. This option requires participants to sign a separate consent form that provides details about the storage and potential future use. The additional sample will be collected at the same time other blood draws are conducted for the main study. No additional visit or venipuncture will be required and no additional compensation will be provided for the optional collection.

Risk/Benefit Assessment

Potential risks: (Phase 2 participants only)

- Electrolyte abnormalities
- Hyperkalemia: the DASH diet is rich in potassium. Urinary excretion of potassium is diminished as kidney function worsens. If severe, hyperkalemia can result in muscle weakness and paralysis, cardiac conduction abnormalities, cardiac arrhythmias, metabolic acidosis and death.

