To evaluate preliminary efficacy of our counseling intervention on DASH adherence, BP, and potassium, we will repeat 24-hour diet recalls, 24-hour urine biomarker studies, office BP, 24-hour ABP, and clinical laboratory studies for all study participants at weeks 12 (post-intervention; primary endpoint) and 24 (after a 3-month post-study observation period; exploratory endpoint). We anticipate that active arm participants will exhibit greater improvement in DASH adherence and a larger reduction in 24-hour mean SBP. Initial summary statistics and graphical displays will be used to make reasonable outcome distribution assumptions. Using an intention to treat, primary analyses to compare the amount of change over time and trajectories of change between the two study arms in DASH diet score, 24-hour mean SBP, and serum potassium will use generalized linear mixed models, with a random effect to capture longitudinal within-person correlation. The primary model for BP outcomes will include study arm, time point, and their interactions, consistent with the randomized trial. Subsequently, a secondary model will be refit to adjust for age, gender, race baseline daily sodium intake, and time-specific values of eGFR, weight, and hypertension medication indicator. Exploratory outcomes in office SBP and DBP, 24-hour DBP, 24-hour urine biomarkers of diet adherence (potassium, phosphorus, urea, and sodium), and additional CKD-relevant metabolic markers (serum phosphorus and bicarbonate) will be assessed using the same analytic strategy. Our analytic approach can be used with any distribution within the exponential family (e.g., normal, binomial, Poisson, and skewed distributions such as gamma and lognormal). The decision on which is most appropriate will be made using initial summary statistics and graphs. The exponential family is broad enough that further transformations of the data are not expected to be necessary, but if so, we will use historically-common transformations to approximate normality. The proportion of participants who do and do not meet safety thresholds (serum potassium >5.2 mg/dl per testing lab standards, phosphorus >5.5 mg/dl, bicarbonate <18 mmol/L) in the two study arms will be compared using the same longitudinal generalized linear mixed model approach, assuming the Binomial distribution.

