Unlike a large clinical trial, our pilot study will not have statistical power to establish the effectiveness and safety of DASH in this population. However, this initial pilot study will generate critical evidence for estimating effect sizes and showing feasibility of the intervention, that will guide future work. Power:

Our power estimate is based on the primary aim comparing treatment arms on the SBP measure. Assuming a 20% attrition rate of 5 per group and using two-sided tests at a type I error rate of 5%, a final sample size of 20 per group will give us 80% power to detect a 7.7 mmHg difference in the change in SBP at 12 weeks between groups, assuming a within-person correlation of 0.7 over time and a standard deviation of SBP of 11 mmHg. A between-group difference of 11.4 and 7.8 mmHg were observed in prior DASH feeding and counseling intervention studies. To assess the sensitivity of the results to any missingness in the data, we will use multiple imputation to create complete cases while incorporating the uncertainty in doing so in the assessment of model parameters. The SAS/STAT software, version 15.1 for Windows and R packages (version 3.6.1) will be used for the data analyses, after extraction from the research database REDCap (Research Electronic Data Capture).

Phase 2c: For this qualitative aim, self-reported barriers and facilitators to DASH diet adherence among active arm participants will be described. Interview transcripts will be analyzed using framework analysis. A thematic analysis approach will be used to allow new concepts to emerge inductively from the data.

Data & Safety Monitoring

Safety monitoring:

Hyperkalemia: Hyperkalemia is the most serious potential risk that CKD patients who follow the DASH diet may experience. Therefore, we plan to actively monitor serum potassium concentrations during the intervention and intensify monitoring during periods that elevations in potassium, if they occur, would most likely be observed. When and how frequently we plan to measure serum potassium has been determined by:

- when participants will be counseled about potassium-rich and potassium-poor foods by the dietitian (i.e., week 2-3);
- knowledge about timing of steady-state concentrations of potassium following increased oral intake; and

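### If the planned random effect is a random intercept fitted across baseline, week 12 and week 24, week-24 variability feeds into the standard error of the primary week-12 SBP contrast

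*Combined protocol and SAP*

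**What the plan says.** The Phase 2b analytic strategy repeats the outcome measurements "at weeks 12 (post-intervention; primary endpoint) and 24 (after a 3-month post-study observation period; exploratory endpoint". The primary analyses are to "compare the amount of change over time and trajectories of change between the two study arms" for DASH score, 24-hour mean SBP and serum potassium, using generalized linear mixed models "with a random effect to capture longitudinal within-person correlation". For blood pressure, "The primary model for BP outcomes will include study arm, time point, and their interactions". The section states no random slope, residual covariance structure, visit-specific variance, robust standard error or degrees-of-freedom method.

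The Power paragraph makes the same simplification. It takes one SD of 11 mmHg and proceeds "assuming a within-person correlation of 0.7 over time", concluding that "a final sample size of 20 per group will give us 80% power to detect a 7.7 mmHg difference" in the 12-week change. The only sensitivity analysis described is multiple imputation, which addresses missing data and not the covariance.

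**The concern.** For a normal outcome, a random intercept with independent residuals is compound symmetry: every visit has the same variance and every pair of visits the same correlation. The model then estimates one residual variance from all visits and uses it for every contrast, including the primary one at week 12.

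There is some reason to doubt that week 24 resembles the earlier visits. Under Study protocol (Aim 2), participants are asked to hold antihypertensive medication and physical activity constant only for the three-month study period. Week 24 comes after three further months outside that period. If individuals diverge in that time, week-24 SBP may be more variable, or less correlated with earlier values, than week-12 SBP. The reverse is also possible.

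At stake are the width of the week-12 interval and the validity of its p-value. The plan says the pilot is meant to supply effect-size estimates for later work, so an interval with the wrong width would mislead that planning.

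**Working it through.** **Inputs from the Power paragraph:** 20 per arm after attrition, SD 11, correlation 0.7, difference 7.7 mmHg, two-sided 5%. **Assumed, because the documents do not give them:** the week-24 SD and the correlations involving week 24.

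**The plan's own figure.** The variance of the baseline-to-week-12 change is 2 × 11² × (1 − 0.7) = 72.6, so its SD is 8.52. The standard error of the difference between arms is √(72.6 × 2/20) = 2.69. Power at 7.7 mmHg is 79.5% by the noncentral t with 38 df (81.5% by the normal approximation). The stated 80% is reproduced for a comparison of change scores.

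**What a random-intercept fit uses.** With complete balanced data, the 72.6 is replaced by the average, over all visit pairs, of the variance of the within-person difference. For visits *i* and *j* that variance is SDᵢ² + SDⱼ² − 2·r·SDᵢ·SDⱼ. With weeks 0, 12 and 24 there are three pairs, and two involve week 24. An unstructured covariance uses the 0–12 pair alone.

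*Example 1, correlation decaying to 0.49 by week 24.* The 0–24 pair gives 2 × 121 × 0.51 = 123.4. The average is (72.6 + 123.4 + 72.6)/3 = 89.5, and the model SE is √(89.5 × 2/20) = 2.99, which is 11% too wide.

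*Example 2, week-24 correlations of 0.75.* Each week-24 pair gives 2 × 121 × 0.25 = 60.5. The average is (72.6 + 60.5 + 60.5)/3 = 64.5, and the model SE is 2.54, which is 6% too narrow.

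Type I error and power come from simulating complete data with at least 20,000 trials per scenario (Monte Carlo standard error near 5%: √(0.05 × 0.95/20,000) = 0.15 points). The random-intercept test has 76 df. Correlations are in the order 0–12, 0–24, 12–24, and SD is 11 unless stated.

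| Scenario | Average pair variance | Model SE | True SE | Type I | Power at 7.7 |
|---|---|---|---|---|---|
| 0.7, 0.7, 0.7 (compound symmetry) | 72.6 | 2.69 | 2.69 | 4.9% | 81% |
| 0.7, 0.7, 0.7; week-24 SD 12 | 77.7 | 2.79 | 2.69 | about 4.2% | 78–79% |
| 0.7, 0.75, 0.75 | 64.5 | 2.54 | 2.69 | 6.5% | not comparable |
| 0.7, 0.49, 0.7 | 89.5 | 2.99 | 2.69 | 3.1% | 74% |
| 0.7, 0.7, 0.7; week-24 SD 15 | 100.9 | 3.18 | 2.69 | 2.1% | 69% |
| 0.7, 0.4, 0.5 | 112.9 | 3.36 | 2.69 | 1.5% | 65% |
| 0.6, 0.6, 0.85 | 76.6 | 2.77 | 3.11 | about 8% | not comparable |

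Power is not comparable where type I error is inflated. Using the 0–12 pair alone gives type I error of about 5% in every row, and power of 79–80% in every row that keeps the 0–12 correlation at 0.7 with SD 11 at both visits.

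**Check on the formula.** Random-intercept models were fitted to simulated data in two more extreme scenarios. For week-24 SD 14 with week-24 correlations of 0.5, the formula gives 3.65 and the mean fitted SE was 3.64. For SD 9 with correlations of 0.8, both are 2.31. The true SE is 2.69 in each.

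**The case against.** The strongest reply is that the text is underspecified and not wrong. It does not say random intercept, and it does not say that week 24 shares the fit used for the primary contrast. If only baseline and week 12 were fitted with complete data, the standard error would be correct. This stands as a limit. The point rests on the ordinary reading of one random effect and on the likely, but not certain, reading that comparing trajectories means one joint model.

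Second, no week-24 SD or correlation appears in the documents, and under the plan's single SD and correlation there is no error. This also stands, so the figures are an assumed range. Inflation does not, however, depend on changing the planned 0.7 between baseline and week 12: keeping it and setting both week-24 correlations to 0.8 gives a model SE of 2.38 and type I error of 8.5%.

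Third, the compensation text refers to "payments for each of the 4 data collection visits", including one at week 4. If SBP from four visits were modelled and correlation decayed smoothly, the model SE would be only 2% to 4% too wide and type I error 4.2% to 4.5%. The Phase 2b text names only weeks 12 and 24 for repeat ambulatory monitoring, so three visits is the more natural reading.

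Some stronger inferences are tempting but unsupported. A reader might take the hypothesised fall in diet quality after week 12 (Purpose of the Study) as proof of unequal variances. It concerns the average, which the arm-by-time terms absorb. A reader might also say that week 24 alone sets the error bars, or that the 5% level is lost whenever week 24 differs. Week 24 supplies two pairs of three, mild departures do little, and a higher SD can be offset by a higher correlation. Finally, that the study is a pilot without power to establish effectiveness lowers the stakes but does not remove them, since its estimates are meant to guide later work.

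**Conclusion.** The point holds in conditional form. If the random effect is an intercept and the three visits share one fit, the standard error of the primary week-12 SBP contrast is partly determined by week 24 and can be wrong in either direction. Type I error is unaffected under compound symmetry, about 4% to 6.5% for mild departures, 3.1% (power 74%) under decay to 0.49, and roughly 1.5% to 8% in the larger departures tabulated.

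These figures assume complete balanced data, normal outcomes and 20 per arm. Under those conditions the week-12 point estimate does not change; the effect under dropout was not examined. The plan's power figure is sound for the comparison of changes, but the planned model is sure to deliver it only if compound symmetry holds. The matter is worth correcting because a better specification costs almost nothing.

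**What to change.** In the Phase 2b analytic strategy, for 24-hour SBP and DASH score at baseline, week 12 and week 24, replace the random effect with an unstructured within-person covariance and Kenward-Roger degrees of freedom. State that the primary estimate is the arm-by-week-12 contrast from that model. Name a fallback for non-convergence: either heterogeneous compound symmetry with small-sample-corrected standard errors (uncorrected robust standard errors are a weak choice at 20 per arm), or a model of baseline and week 12 only.

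For serum potassium, apply this only to visits scheduled in both arms. Data & Safety Monitoring schedules potassium for the intervention arm at weeks 0, 2, 4, 8 and 12. Adding week 24 makes six visits and 6 × 7/2 = 21 covariance parameters, too many to estimate reliably here.

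The cost is a short change of text and a standard software option. With three visits there are six covariance parameters in place of two, so four more, and about 1 point of power is lost if compound symmetry is true (80.6% to 79.5%). No new data or visits are needed.

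### Free improvement, not an error: constraining the two arms to a common baseline mean in the primary SBP model would cut the variance of the week-12 difference by about 11-12% at the plan's own assumptions

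*Combined protocol and SAP*

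**What the plan says.** The Phase 2b analytic strategy uses mixed models with a per-person random effect. It describes "primary analyses to compare the amount of change over time and trajectories of change between the two study arms" for DASH score, 24-hour mean SBP and serum potassium. For blood pressure it adds: "The primary model for BP outcomes will include study arm, time point, and their interactions, consistent with the randomized trial". Then "a secondary model will be refit to adjust for age, gender, race baseline daily sodium intake", together with visit-specific eGFR, weight and an indicator for hypertension medication. Neither model states that the arms share a baseline mean. The levels of the time-point factor are not listed; the post-baseline assessments are at "weeks 12 (post-intervention; primary endpoint) and 24 (after a 3-month post-study observation period; exploratory endpoint".

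The power paragraph claims "80% power to detect a 7.7 mmHg difference in the change in SBP at 12 weeks between groups" with 20 per group, "assuming a within-person correlation of 0.7 over time and a standard deviation of SBP of 11 mmHg". On dropout it says: "Assuming a 20% attrition rate of 5 per group". The Aim 2 design fixes 50 participants, randomised 1:1. Of the purpose, the plan says "this initial pilot study will generate critical evidence for estimating effect sizes and showing feasibility of the intervention".

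**The concern.** With arm, time and arm-by-time terms, and baseline among the time points, the arm main effect is the baseline difference between arms. The week-12 treatment effect is then the week-12 difference minus a weighted share of the observed baseline difference. Randomisation already tells us that the expected baseline difference is zero. Estimating it freely adds noise to the contrast that matters.

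What is at stake is precision alone. One stated purpose of the pilot is to estimate effect sizes for later work, and a narrower interval from the same data serves it. The other purpose, feasibility, and the recruitment and acceptability criteria under Phase 2a are untouched.

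**Working it through.** **Inputs.** From the power paragraph: SD σ = 11 mmHg, within-person correlation ρ = 0.7, two-sided 5% test, 20 completers per arm after losing 5. From the Aim 2 design: 50 randomised 1:1, so 25 baselines per arm. I take the SD and correlation to apply to 24-hour mean SBP, the primary blood pressure outcome.

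**Step 1: reproduce the plan's figure.** SD of change = 11 × √(2 × (1 − 0.7)) = 8.52 mmHg. With 20 per arm and a 7.7 mmHg difference, power is 81.5% (normal) or 79.5% (noncentral t). The stated 80% reproduces. A comparison of week-12 values alone (SD 11) would give 60%, and an SD adjusted for baseline would need only 17 per arm. The power basis is therefore the unadjusted change score.

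**Step 2: variance under the planned model.** With n baselines and m week-12 values per arm, the mixed model also uses the dropouts' baselines, and

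Var = 2σ² × [(1 − ρ²)/m + (1 − ρ)²/n] = 242 × (0.51/20 + 0.09/25) = 7.04.

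SE = 2.65; 95% half-width (t, 38 df) 5.37; power at 7.7 mmHg 80.7%.

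**Step 3: common baseline mean.** The second term drops out:

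Var = 242 × 0.51/20 = 6.17, a saving of 1 − 6.17/7.04 = 12.4% with the correlation known. Exact generalised least squares gives the same saving with week 24 added.

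**Step 4: baseline as covariate.** Estimating the slope costs a factor 1 + 1/(2m − 4) = 1 + 1/36:

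Var = 6.171 × 1.0278 = 6.34, a saving of 9.9%. SE = 2.52; half-width 5.10; power 84.5%.

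**Step 5: estimate everything.** Simulation used 25 baselines and 20 week-12 values per arm, normal data, dropout completely at random and REML random-intercept fits. There were 40,000 null runs and 20,000 runs at 7.7 mmHg.

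| | Planned | Common baseline | Covariate |
|---|---|---|---|
| Variance (null runs) | 7.04 | 6.24 | 6.33 |
| Saving (null; 7.7 mmHg) | – | 11.3%; 11.6% | 10.1%; 10.7% |
| Type I error | 0.050 | 0.051 | 0.049 |
| Power at 7.7 mmHg | 80.8% | 85.5% | 84.2% |
| Mean half-width, mmHg | 5.33 | 4.97 | 5.06 |

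Like for like, the common-baseline half-width falls by 0.36 mmHg in simulation. By formula it falls by 0.31: from 5.37 to √6.24 × 2.024 = 5.06. In completers, the gain is worth 7.04/6.33 = 1.11 to 7.04/6.24 = 1.13, or 11-13% more.

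**Step 6: sensitivity.**

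- Correlation 0.5 / 0.6 / 0.8 / 0.9 (simulated): common baseline 20% / 15% / 8% / 4%; covariate 19% / 14% / 7% / 1.5%.
- Fewer randomised, assuming 80% retention, covariate form: 16 of 20 per arm, 1 − (0.51/16 × 29/28)/(0.51/16 + 0.09/20) = 9.2%; 12 of 15 per arm, 1 − (0.51/12 × 21/20)/(0.51/12 + 0.09/15) = 8.0%.
- Clustering by counselling group (illustrative assumption: 4-5 groups in the intervention arm, between-group variance 2-10% of 121). This adds 2.42/5 = 0.48 to 12.1/4 = 3.03 to both variances. The common-baseline saving becomes 0.80/7.52 = 11% down to 0.80/10.07 = 8%. The covariate saving becomes 0.70/7.52 = 9% down to 0.70/10.07 = 7%.

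**The case against.** The planned model is a standard, unbiased analysis, the gain is about 0.3 mmHg on a 5.4 mmHg half-width, and no decision rule in the plan turns on it. The plan itself says that the pilot cannot establish effectiveness. All of that stands. It is why this is offered as an improvement and not as a correction. It does not remove the case for a more precise estimate from data already collected.

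Three stronger readings are tempting, and the documents do not support them.

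- *A reader might infer that the plan ignores baseline SBP because it is in neither covariate list.* If baseline is a modelled time point, baseline SBP is already an outcome row and the random effect uses it, including for dropouts. It would not normally be a covariate as well. Only the common-mean constraint is missing.
- *A reader might infer that baseline is not modelled at all.* The gain would then be about 48-49%, because the planned variance would be proportional to 1/20 = 0.0500 per arm, against 0.0255 or 0.0262. The time points are not listed, so this cannot be excluded outright. But the stated comparison is of change, and the power figure matches a change score (60% for week-12 values alone), so the text favours the other reading.
- *A reader might quote a 15% saving.* That holds only with no dropout and a known correlation.

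A further objection also stands: the plan says the study was ended while Cohort 5 was being screened, and it does not give the number randomised. The headline saving therefore rests on planned numbers.

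**Conclusion.** The point holds as a modest efficiency gain. At SD 11, correlation 0.7, 25 randomised and 20 completing per arm, and independent participants, the variance of the week-12 SBP difference falls by about 11-12% with a common baseline mean, or 10-11% with baseline as covariate. The 95% half-width goes from about 5.4 to about 5.0-5.1 mmHg, and type I error is unchanged.

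The conclusion rests on the inference that baseline is a modelled time point, and its size rests on the assumed correlation. At a correlation of 0.8 to 0.9 the saving runs from about 8% down to 1.5%. With fewer randomised, the covariate form saves 8-9%. Under modest assumed clustering by counselling group the saving is about 7-11%. None of this shows bias or inadequate power, and the stated sample size and detectable difference can stand. For DASH score and potassium the documents give no SD or correlation, so no saving can be computed.

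**What to change.** In the Phase 2b analytic strategy, for 24-hour mean SBP:

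- List the modelled time points, including baseline.
- Replace the free baseline arm effect with a common baseline mean, and fit arm-by-visit terms for the post-baseline visits only. This is preferred because it keeps change and its trajectory in the model. The alternative is to model the post-baseline values with baseline SBP as covariate.
- Keep the week-12 arm difference as the primary contrast.
- Date the choice and state that it was made before outcomes by arm were seen. If they have been seen, keep the planned model as primary and report this one as a labelled supportive analysis.

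The cost is a short change to the analysis text, with no new data, visits or participants. The covariate form uses one degree of freedom, already counted above.

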Study participants who were randomized to the control group will have the opportunity to attend 6 weekly virtual diet information sessions after they complete final data collection visits and exit the study. Only participants whose schedules are compatible with course offerings by the dietitian will be able to attend. Diet information will align with national professional kidney organization recommendations. No research or monitoring data will be collected on participants who attend the 6-week session block. Invitations to participant in the post-study diet sessions will be mailed and/or emailed to former participants. Participants may also be contacted by phone by study staff and invited to participate.

Opportunity for participants who were screening for Cohort 5 during study cancellation:

We will provide an opportunity for study participants who were in the midst of screening for Cohort 5 to attend the diet counseling sessions that they otherwise would have received had we not ended the study. This will involve a one-on-one virtual diet session and 6 virtual diet group sessions led by the study dietitian, which is the same amount of access to the study dietitian that the control group was offered during the study. Participants will complete an in-center screening visit, per protocol, to confirm that it is safe to attend counseling sessions. Those who pass screening, thereby demonstrating that their blood pressure and labs meet original inclusion criteria, will be invited to participate in diet sessions only. Only participants whose schedules are compatible with course offerings by the dietitian will be able to attend. Diet information provided during the sessions will align with national professional kidney organization recommendations. Other than data collected during the screening visit, no research or monitoring data will be collected on participants who attend the 6-week session block. Because this activity is not a part of the research and does not involve an intervention, study participants will not be reconsented.

Selection of Subjects

Aim 1 Inclusion Criteria:

- Black race (self-identified)
- ≥ 21 years old
- CKD defined as an eGFR of 20-59 ml/min/1.73m²
- acknowledges self-awareness of CKD diagnosis
- Exclusion Criteria
- History of kidney transplant
- Lack of English language proficiency

Aim 2 Inclusion Criteria:

- Black race (self-identified)
- ≥ 21 years old
- CKD defined as an eGFR of 20-59 ml/min/1.73m²
- SBP ≥ 100 mm Hg

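### Age, gender and baseline sodium, entered as main effects, effectively do not adjust the arm difference in SBP change in the secondary model, and race cannot vary (minor)

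*Combined protocol and SAP*

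**What the plan says.** The Phase 2b analytic strategy sets out to "compare the amount of change over time and trajectories of change between the two study arms", and the analyses "will use generalized linear mixed models, with a random effect to capture longitudinal within-person correlation". For blood pressure: "The primary model for BP outcomes will include study arm, time point, and their interactions". Then "a secondary model will be refit to adjust for age, gender, race baseline daily sodium intake". The same sentence also lists eGFR, body weight and an indicator of antihypertensive medication, each taken at its value for the visit. No interaction is mentioned for any covariate, and the text does not say outright that the covariates enter as main effects only. The outcome distribution is left open: "Our analytic approach can be used with any distribution within the exponential family".

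The Power paragraph sizes the study on a "difference in the change in SBP at 12 weeks between groups". Together with the stated interest in change over time, this implies that baseline SBP is one of the modelled time points.

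Under Selection of Subjects, the first Aim 2 inclusion criterion is self-identified Black race.

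**The concern.** The quantity of interest is the difference between arms in SBP change, which is the arm-by-time term. A covariate with one value per person, entered without a time interaction, explains differences in level between people. It does not explain differences in change, so it can neither correct a chance imbalance in that contrast nor sharpen it.

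With about 20 completers per arm and no stratification described, some imbalance in a factor such as sodium intake is plausible. The pilot is meant to supply effect sizes for later work, so an estimate labelled as adjusted for baseline sodium should be adjusted for it. If the primary and secondary models agree, that agreement says almost nothing about age, gender or sodium. If they differ, the difference comes mainly from the time-specific eGFR, weight and medication terms.

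**Working it through.** **Inputs from the plan.** 50 randomized 1:1, 5 lost per arm, 20 completers per arm, SD 11 mmHg, within-person correlation 0.7, two-sided 5%, target 7.7 mmHg, visits at weeks 0, 12 and 24. Covariate effects and dropout mechanisms in the simulations are assumptions.

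**The plan's own figure.** SD of change = 11 × √(2 × (1 − 0.7)) = 8.52 mmHg. With 20 per arm the standard error of the difference is 8.52 × √(2/20) = 2.69 mmHg. Power for 7.7 mmHg is 81.5% by the normal approximation and 79.5% by the noncentral t with 38 df. The stated 80% is reproduced, and it uses no covariates.

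**Algebra.** For person i at visit t, with arm A, baseline covariates X and random intercept b:

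Y(i,t) = μ + αA(i) + τ(t) + δ(t)A(i) + γX(i) + b(i) + e(i,t)

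Y(i,12) − Y(i,0) = [τ(12) − τ(0)] + [δ(12) − δ(0)]A(i) + e(i,12) − e(i,0)

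Both γX(i) and b(i) cancel. With complete data the arm-by-time estimate is the difference in mean change, whether or not X is in the model.

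**Size of the departure from exact cancellation.** Normal random-intercept model, REML, 200 simulated trials per scenario. The table gives the movement in the week-12 arm-by-time estimate when age, gender and baseline sodium are added as main effects:

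| Setting | Mean absolute shift (mmHg) | Largest |
|---|---|---|
| Complete data, no time-varying covariates | 0.00 | 0.00 |
| Complete data, time-varying eGFR and weight | 0.14 | 0.94 |
| 5 baseline-only dropouts per arm, no time-varying covariates | 0.12 | 0.45 |
| About 20% dropout related to sodium, no time-varying covariates | 0.16 to 0.18 | 0.73 |
| About 20% dropout related to sodium, time-varying eGFR and weight | 0.20 to 0.21 | 0.89 |

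The standard error was about 2.6 to 2.8 mmHg throughout. Its mean change was at most 0.02.

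**Do these small shifts remove an imbalance?** An imbalance of 0.5 SD in baseline sodium was imposed, with a true effect of 0, 20% dropout, time-varying eGFR and weight, and an assumed sodium effect of 0.3 or 0.5 SD of change per SD of sodium (120 trials each). Mean week-12 estimates:

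| Model | Effect 0.3 | Effect 0.5 |
|---|---|---|
| No baseline covariates | 1.40 | 2.05 |
| Baseline main effects | 1.41 | 2.08 |
| Covariate-by-time terms | 0.18 | −0.02 |

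Main effects removed none of it. Simple arithmetic predicts shifts of the same order: 0.3 × 0.5 × 8.52 = 1.28 and 0.5 × 0.5 × 8.52 = 2.13 mmHg, or 17% and 28% of 7.7.

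**How likely is such an imbalance?** The standardized baseline difference has SD √(2/20) = 0.316. The chance that it exceeds 0.5 in either direction is 11% for one covariate, and 1 − 0.886³ = 30% for at least one of three independent covariates.

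**Race.** Under the inclusion criterion every Aim 2 participant has the same value, so a race coefficient cannot be estimated in any form of the model.

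**The case against.** A reader might infer that the secondary SBP result is not adjusted for these factors at all. The documents do not support that, for four reasons. The plan says only that it will adjust, and covariate-by-time terms would be consistent with that wording. It expects 20% attrition, so the data will not be complete. The same model carries time-specific eGFR, weight and medication, whose coefficients depend on which baseline terms are present. And it allows distributions whose link would break exact cancellation. All four stand, so exact cancellation cannot be claimed for the model as planned. They do not rescue the adjustment on the main-effects reading: in the settings simulated, the resulting shifts are small and do not reduce an imbalance. The effect of a non-identity link was not quantified.

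A reader might also infer a bias of 1.3 to 2.1 mmHg. That does not follow. The figure needs an imbalance with an 11% chance per covariate and a correlation between sodium and SBP change that the documents do not give. Over repeated randomizations the arm contrast is unbiased, and its standard error already allows for chance imbalance.

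Finally, the plan nowhere says that agreement between the two models will be presented as robustness, and it states that the pilot is not powered to establish effectiveness or safety. Both points are fair and keep this minor. Software that drops a constant term would also make listing race harmless in practice, though it still should not be listed as an adjustment.

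**Conclusion.** The point holds as a minor one, confined to the secondary analysis. On the natural reading of the plan (baseline SBP as a modelled time point, interactions only for arm by time, an approximately normal outcome), age, gender and baseline sodium effectively do not adjust the between-arm difference in SBP change. Race cannot be adjusted for on any reading.

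The primary model, its randomized contrast and the sample size stand as written. How much a properly specified adjustment would gain depends on how strongly these covariates predict SBP change, on which the documents are silent.

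**What to change.** In the secondary blood pressure model, enter baseline sodium intake with its interaction with time point. Do the same for age and gender if adjustment for them is wanted. Delete race.

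This is one sentence of plan wording and needs no new data. It adds one parameter per follow-up visit for each interacted covariate. If the covariates do not predict SBP change, the variance of this estimate rises by about 2.5% for sodium alone (simulated ratio 1.025) or about 9% for all three (1.087). All three pay for themselves once they explain roughly 1 − 1/1.087 = 8% of the variance in SBP change. At an assumed correlation of 0.5 the variance instead falls by about 25% (sodium alone) or 20% (all three).

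A week-12 analysis that conditions on baseline SBP and includes these covariates would also adjust the contrast. It is a different estimator, not an equivalent one: at correlation 0.7 its residual variance is proportional to 1 − 0.49 = 0.51, against 2 × (1 − 0.7) = 0.60 for change. If it is preferred, the plan should say so explicitly.
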